### **3.5. Premature Discontinuation from Study Treatment**

If a subject has discontinued all study treatments prior to definitive disease progression, the subject shall remain on study until at least 1 of the criteria for discontinuation from study is met (Section 3.6). Every attempt should be made to keep the subject in the study and continue to perform tumor evaluation by CT or MRI every 8 weeks until disease progression. If this is not possible or acceptable to the subject or investigator, the subject may be withdrawn from the study. It is recommended that the investigator consults with the medical monitor prior to removing the subject from study for any reason except subject withdrawal of consent.

### **3.6. Discontinuation Criteria from Study**

Subject study participation will be ended due to any of the following reasons, and subjects should then enter long-term follow-up if applicable:

- Initiation of non-study specific anti-neoplastic therapy in the absence of progression
- Disease progression
- Intercurrent illness that would, in the judgment of the investigator, affect assessments of clinical status to a significant degree
- Withdrawal of consent.

— A subject may withdraw consent solely from active participation in the study but participate in follow up for survival

- Investigator decision to remove the subject from the study, in consultation with Gilead Medical Monitor
- Death
- Discontinuation of the study at the request of Gilead, a regulatory agency, or an IRB/IEC
- Lost to follow up

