### 6.2.9. Disease and Response Assessment

#### 6.2.9.1. Tumor Imaging

Either contrast-enhanced CT or gadolinium-enhanced MRI of the chest, abdomen, and pelvis will be performed at screening, every 8 weeks during the study (starting from Cycle 1 Day 1) and at the EOS visit if one has not been performed within the last 8 weeks. Tumor burden will be evaluated solely based on radiographic imaging per RECIST v 1.1. Chest x-ray, ultrasound, endoscopy, laparoscopy, positron-emission tomography, radionuclide scans, or tumor markers will not be considered for response assessment.

For radiographic evaluations, the same method of assessment and the same technique (eg, scan type, scanner, subject position, dose of contrast, injection/scan interval) should be used to characterize each identified and reported lesion at baseline and during study treatment and follow-up.

Scans taken as part of standard medical practice up to 42 days prior to randomization can be used for Screening as long as they meet all study requirements. During the treatment phase, scans may be performed at time points other than every 8 weeks as clinically indicated to assess tumor progression.

For subjects who stop study treatment in the absence of disease progression (eg, experienced unexpected toxicity), scans should continue to be collected approximately every 8 weeks until disease progression or initiation of systemic anti-tumor therapy other than the study treatment, whichever is earlier.

All relevant clinical and radiographic information required to make each assessment must be made available for source verification and submission to a central reader. Scans will be transferred to a central reader for collection and future analysis. Disease progression will be determined by the investigator or qualified designee.

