### **6.3. Assessments for Premature Discontinuation from Study**

If a subject has discontinued all study treatments prior to definitive disease progression, the subject shall remain on study for follow-up for progression-free survival (see Sections 3.5 and 3.6). Every attempt should be made to keep the subject in the study and continue to perform tumor evaluation by CT or MRI every 8 weeks. Subjects will remain on study until disease progression or initiation of non-study specific anti-neoplastic therapy in the absence of progression, whichever occurs earlier.

If it is not possible to keep the subject on study, or acceptable to the subject or investigator, the subject may be withdrawn. It is recommended that the investigator consults with the medical monitor prior to removing the subject from study for any reason except subject withdrawal of consent.

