## **6.2. Secondary Efficacy Endpoint**

### **6.2.1. Definition of the Secondary Efficacy Endpoints**

#### **6.2.1.1. Progression-Free Survival**

Progression-free survival is defined as the time interval from the date of randomization to the earlier of the first documentation of definitive disease progression or death from any cause. All scans, whether scheduled or unscheduled, will be considered.

The date of definitive progression will be the time point at which progression is first identified by relevant radiographic imaging data. Data will be censored on the date of last adequate tumor assessment for subjects (including assessments with a not evaluable [NE] outcome):

- who do not have disease progression or die before study discontinuation, or
- who start new anticancer therapy prior to documented disease progression or death, or
- who have  $\geq 2$  consecutive missing tumor assessments before disease progression or death

If a subject does not have a baseline tumor assessment, then PFS will be censored at Study Day 1, regardless of whether or not definitive progression or death has been observed.

PFS in months will be calculated by  $(\text{date of event/censoring} - \text{date of randomization} + 1) / 30.4375$ .

When imaging examinations for one visit are conducted on various dates, the following rules apply for the calculation of the assessment date:

- The response date will be the last date associated with that particular imaging time point.
- The progression date will be the first date associated with that particular imaging time point.

When the date of initiation of anticancer therapy other than the study treatment is incomplete or missing, the following algorithm will be followed:

- If the day is missing but the month and year are available, then the imputed day will be the last day of the month.
- If day and month are missing but year is available, then the imputed day and month will be 01Jan or the last day of the month for the last adequate disease assessment if they have the same year, whichever is later.

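### Protocol 3.6 ends the 8-weekly scans for intercurrent illness without progression, in conflict with 6.3, 6.2.9.1, Appendix 2 and the synopsis, and so permits prognosis-linked censoring of PFS

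*Protocol*

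**What the plan says.** - **Exit rule, protocol 3.6.** "Subject study participation will be ended due to any of the following reasons". The list includes "Intercurrent illness that would, in the judgment of the investigator, affect assessments of clinical status to a significant degree" and "Investigator decision to remove the subject from the study, in consultation with Gilead Medical Monitor". Neither requires progression. The illness line appears word for word in 3.4 as a reason to stop treatment.
- **After exit.** Meeting any 3.6 criterion triggers the EOS visit (6.6), with a CT or MRI if none was done in the previous 8 weeks (6.2.9.1). Long-term follow-up is then a phone call every 3 months for survival status and later therapy (6.8). No scans are scheduled.
- **Staying on study, protocol 6.3, first paragraph.** For subjects who stop all treatment before progression: "Subjects will remain on study until disease progression or initiation of non-study specific anti-neoplastic therapy in the absence of progression, whichever occurs earlier".
- **Scanning, protocol 6.2.9.1.** After treatment stops, "scans should continue to be collected approximately every 8 weeks until disease progression or initiation of systemic anti-tumor therapy other than the study treatment", whichever comes first. An Appendix 2 footnote gives the same two end points. The synopsis follows subjects who stop study drug until progression is documented and names no other end point.
- **Permitted withdrawal.** Protocol 3.5 keeps the subject on study until a 3.6 criterion is met. Both 3.5 and the second paragraph of 6.3 allow removal; 6.3 says: "If it is not possible to keep the subject on study, or acceptable to the subject or investigator, the subject may be withdrawn".
- **Censoring.** SAP 6.2.1.1 censors PFS at the last adequate tumor assessment for subjects "who do not have disease progression or die before study discontinuation", and for those with two or more consecutive missing assessments before the event. Protocol 8.4.1 censors survivors without progression and applies the same missed-assessment rule.
- **Status of PFS.** It is the first gated secondary endpoint, tested at one-sided 0.016 once OS is rejected (protocol 8.5.3).

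**The concern.** One event, an illness judged to disturb clinical assessment, can stop treatment under 3.4 and also end measurement under 3.6. Progression here is judged on imaging alone (6.2.9.1), so a disturbed clinical picture does not by itself prevent PFS from being measured. Subjects who become that ill may well be closer to progression or death than those who stay. If so, censoring them is not independent of the outcome, and their events drop out of the analysis. PFS carries controlled alpha, so both lost power and a distorted hazard ratio would matter.

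**Working it through.** **1. The passages side by side, for a subject who stops all treatment through intercurrent illness before progression**

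| Place | What happens to scans |
|---|---|
| 3.6 with 6.6 and 6.8 | Participation ends; EOS scan if none in the previous 8 weeks; then phone calls only |
| 6.3, first paragraph | Stays on study to progression or new therapy |
| 6.2.9.1 | 8-weekly scans to progression or new therapy |
| Appendix 2 footnote | Same as 6.2.9.1 |
| Synopsis | Followed to documented progression |

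The first row cannot be reconciled with the other four.

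**2. What becomes of PFS after such an exit**

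Progression seen on the EOS scan counts. Otherwise scanning has stopped and the subject is generally censored at the last adequate assessment. A later death is unclear. If study discontinuation in SAP 6.2.1.1 means a 3.6 exit, the death is not a PFS event. Under protocol 8.4.1 it is, unless two or more assessments were missed first. If unscanned visits count as missed, that cuts off deaths later than about 2 x 8 = 16 weeks after the last scan.

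**3. The plan's own PFS figure**

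Inputs (protocol 8.11): 215 per arm, control median 9 months, HR 0.70, accrual 18 months, follow-up 18 months, dropout 10% a year, one-sided alpha 0.016 (z = 2.144).

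Expected events per arm = 215 x the average over entry time u in (0, 18) of [λ/(λ+δ)] x [1 − exp(−(λ+δ)(36−u))]. Here λ = ln 2/9 for control, 0.7 times that for GS-5745, and δ = −ln(0.9)/12. The total is 321.0, or 322.4 with δ = 0.10/12. The plan states 322.

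Power = Φ(−ln(HR) x √D/2 − z) = Φ(0.3567 x 17.944/2 − 2.144) = Φ(1.056) = 85.4%. The plan states 85%. Both figures reproduce, so the sample size is not in error.

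**4. Equal loss in both arms (assumed rates)**

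D = 322 x (1 − q), HR unchanged at 0.70:

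| q | Events | Power |
|---|---|---|
| 5% | 306 | 83.5% |
| 10% | 290 | 81.4% |
| 15% | 274 | 79.0% |
| 20% | 258 | 76.4% |

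**5. Unequal loss (assumed rates)**

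If a fraction q of each arm's events is removed just before it occurs, observed HR ≈ true HR x (1 − qT)/(1 − qC), where T is GS-5745 and C is control.

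- Null, 10% on GS-5745 and 5% on control: HR = 0.90/0.95 = 0.947; D = 322 x 0.925 = 298; rejection = Φ(0.0541 x √298/2 − 2.144) = 4.7%.
- True HR 0.70, 5% on GS-5745 and 10% on control: HR = 0.70 x 0.95/0.90 = 0.739; power = Φ(0.3026 x √298/2 − 2.144) = 68%.

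The 298 starts from the 322 events expected at HR 0.70; under the null more events would occur. A log-rank simulation avoids this shortcut. It used 4000 runs per case, exponential times and the inputs above, with exiting subjects censored at the last 8-weekly scan before their event:

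| True HR | Exits GS-5745 / control | Events | Estimated HR | Rejection at 0.016 |
|---|---|---|---|---|
| 1.00 | 0 / 0 | 344 | 1.00 | 1.8% |
| 1.00 | 5% / 5% | 327 | 1.00 | 1.7% |
| 1.00 | 10% / 10% | 310 | 1.00 | 2.0% |
| 1.00 | 10% / 5% | 318 | 0.95 | 4.3% |
| 1.00 | 5% / 10% | 318 | 1.05 | 0.3% |
| 0.70 | 0 / 0 | 321 | 0.70 | 85.3% |
| 0.70 | 10% / 10% | 289 | 0.70 | 80.7% |
| 0.70 | 5% / 10% | 297 | 0.73 | 68.5% |

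Monte Carlo standard error is about 0.2 points in the no-exit null case. The equal-exit null rows do not differ from it beyond noise.

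**The case against.** Several stronger readings are tempting, and the documents do not support them.

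- **That the investigator-decision ground also contradicts 6.3.** It does not. Sections 3.5 and 6.3 both refer to 3.6 and both allow withdrawal when staying is not acceptable to the investigator. The clash concerns the illness line, where a mandatory exit meets a narrower list of end points.
- **That whatever stops treatment also stops scanning.** Adverse events and subject request are in 3.4 but not in 3.6, and the two investigator lines differ: one removes the subject from treatment, the other from the study.
- **That plain disease progression in 3.6 lets a clinical call end scanning.** Sections 6.3 and 6.2.9.1 use the same plain words, and 6.2.9.1 judges tumor burden by imaging alone.
- **That every exit loses its event.** The EOS scan looks for progression at exit. SAP 4.1 lists stopping lesion assessment separately from leaving the study, which there includes survival follow-up. On that usage an early death after exit could still be a PFS event.
- **That the PFS error rate is 4 to 5%.** That figure needs a 2:1 imbalance for which the documents give no basis, in a double-blind trial with the same procedures in both arms. It also describes the PFS test taken alone; a false PFS claim further requires OS to be rejected.

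Two more points limit the size. The 10% annual dropout may already cover some of these exits. The list of PFS sensitivity analyses in SAP 6.2.4 is not in the supplied text, so nothing can be said about whether they address this.

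What survives is the textual conflict and its consequence: a site that follows 3.6 stops collecting PFS data for a reason that may be tied to prognosis. Dropout allowances do not deal with that link, and no analysis can recover scans that were never taken.

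**Conclusion.** The conflict between 3.6 and the other four places is real for intercurrent illness. It permits prognosis-linked censoring of an alpha-controlled endpoint; it does not show that bias is built in. Neither the rate nor the direction of any imbalance can be found in the documents.

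Under assumed equal exits of 10% per arm, the cost is power, from about 85% to about 81%, with the hazard ratio unbiased. Error or bias in the hazard ratio arises only if exits differ between arms, and it can go either way. The unequal cases are illustrations. They also take the severe form in which each exit removes an event that was about to happen. OS, the primary endpoint, is protected because survival follow-up continues after exit. This is a point the sponsor should correct, not one that undermines the trial.

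**What to change.** - Reconcile protocol 3.5, 3.6, 6.2.9.1, 6.3, Appendix 2 and the synopsis so that meeting the intercurrent-illness criterion does not by itself end tumor assessment. Scans would continue where feasible until RECIST v1.1 progression, death, new anticancer therapy or withdrawal of consent for scans.
- Leave 3.4 unchanged. The point concerns measurement, not when treatment stops.
- Align SAP 6.2.1.1 with protocol 8.4.1 on whether a death after scanning stops is a PFS event. State whether study discontinuation there means a 3.6 exit or the end of all follow-up, and whether visits no longer scanned count as missing assessments.

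The cost is wording, plus a few extra scans in ill subjects, which 6.2.9.1 already calls for. Subjects can still decline.

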### **3.7. Long-Term Follow-Up for Overall Survival and Study Completion**

After the End of Study (EOS), long-term follow-up (LTFU) will be initiated for subjects who discontinue from study due to reasons other than death. The subject shall remain on LTFU for OS until:

- Death
- Withdrawal of consent to participate in LTFU
- Lost to follow up
- End of LTFU period

Every attempt should be made to keep the subject in the LTFU for OS.

The end of the trial will be defined as when all subjects have completed LTFU or discontinued their participation in the study due to death, withdrawal of consent or lost to follow up.

### **3.8. Source Data**

The subject identification number and randomization number captured by the interactive web response system (IWRS), as well as the patient reported outcomes data captured are considered source data.

### **3.9. Biomarker Testing**

#### **3.9.1. Biomarker Samples to Address the Study Objectives**

The biological specimens described below will be collected in this study and will be used to evaluate the association of exploratory systemic and/or tissue specific biomarkers with study drug response including efficacy, as well as to increase knowledge and understanding of the mechanism of action of drug activity in human tumors, biology of resistance and highlight possible new combination opportunities. The specific analyses may include, but will not be limited to, the biomarkers and assays listed below. Because biomarker science is a rapidly evolving area of investigation, it is not possible to specify prospectively all tests that will be done on the specimens provided. Testing may be modified during or after the end of the study to remove tests no longer indicated and/or to add new tests based upon the growing state of the art knowledge.

These samples will be destroyed no later than 10 years, or as per local regulations, after the end of study unless the subject gives specific consent for the remainder of the samples to be stored for optional future research. If the patient provides consent for optional future research, the samples will be destroyed no later than 15 years after the end of the study, or as per local regulations.

##### **3.9.1.1. Pharmacodynamic**

CCI [REDACTED]

##### **3.9.1.2.**

CCI [REDACTED]

**Table 3-1. Biomarker Objectives and Testing**

SAMPLE TYPE	OBJECTIVE	TEST
Blood	To evaluate pharmacodynamics of GS-5745	MMP9 cleavage products (eg, C1M, C4M) Circulating MMP9 protein
	To evaluate the effect of GS-5745 and chemotherapy on inflammation	Circulating cytokines and inflammatory markers (eg, interleukin-8, interleukin-2 receptor, interleukin 6, interferon gamma, etc)
	To evaluate the effect of GS-5745 and chemotherapy on circulating immune cells	Immune monitoring assay
	To evaluate other biomarkers of GS-5745 activity	Circulating growth factors (eg, vascular endothelial growth factor , epidermal growth factor etc)
	To evaluate disease burden and identify mutations correlated with resistance to therapy	Circulating tumor DNA isolation and sequencing for disease-specific markers (eg, mKRAS, mEGFR, mPIK3CA etc) and other genes
Tissue Biopsy: Archival Tissue	To evaluate baseline markers that correlate with response	MMP9, other MMPs and Immune Cells by immunohistochemistry (IHC) Gene expression patterns (RNA) DNA mutations may be evaluated
Tissue Biopsy: At progression (if medically feasible)	To evaluate markers of response or resistance	MMP9, other MMPs and Immune Cells by IHC Gene expression patterns (RNA) and DNA mutations may be evaluated and compared with data from the archival biopsy

**3.9.2. Optional Blood Sample for Future Genomic Analysis**

CCI

**3.9.3. Biologic Samples for Optional Future Research**

CCI

## 4. SUBJECT POPULATION

### 4.1. Number of Subjects and Subject Selection

Approximately 430 subjects will be randomized to receive double-blind study drug. The target population is subjects with previously untreated advanced gastric or GEJ adenocarcinoma.

### 4.2. Inclusion Criteria

Subjects must meet all of the following inclusion criteria to be eligible for participation in this study.

- 1) Male or female  $\geq 18$  years of age
- 2) Histologically confirmed adenocarcinoma of the stomach or GEJ with inoperable, locally advanced or metastatic disease, not amenable to curative therapy

Adenocarcinoma of the GEJ is defined as tumors that have their center within 5 cm proximal and distal of the anatomical esophagogastric junction as described in Siewert's classification system

- 3) Eastern Cooperative Oncology Group (ECOG)  $\leq 1$
- 4) Measurable disease or non-measurable but evaluable disease, according to RECIST v1.1. Subjects with peritoneal disease would generally be regarded as having evaluable disease and allowed to enter the trial
- 5) Subjects not receiving anticoagulant medication must have an international normalized ratio (INR)  $\leq 1.5$  and activated partial thromboplastin time (aPTT)  $\leq 1.5$  X upper limit of normal (ULN)

The use of full-dose oral or parenteral anticoagulants is permitted as long as the INR or aPTT is within therapeutic limits (according to the medical standard in the institution) and the subject has been on stable dose of anticoagulants for at least 1 week at the time of randomization.

- 6) Adequate hematologic function:
  - a) neutrophils  $\geq 2.0 \times 10^9/L$
  - b) platelets  $\geq 100 \times 10^9/L$
  - c) hemoglobin  $\geq 9$  g/dL

- 7) Adequate hepatic function:
  - a) Direct or total bilirubin  $\leq 1.5 \times$  ULN.
  - b) ALT and AST  $\leq 2.5 \times$  ULN, in case of liver metastases  $\leq 5 \times$  ULN
- 8) Creatinine clearance ( $CL_{cr}$ ) should be  $\geq 30$  mL/min based on the Cockcroft -Gault formula. Subjects with a  $CL_{cr}$  just below 30 mL/min may be eligible if a measured  $CL_{cr}$  (based on 24 hour urine collection or other reliable method) is  $\geq 30$  mL/min
- 9) For female subjects of childbearing potential, willingness to use a protocol-recommended method of contraception from the screening visit throughout the study treatment period, for 90 days following the last dose of study drug (GS-5745/placebo), and for 4 months after the last dose of oxaliplatin or 6 months after the last dose of 5-FU whichever occurs later unless the subject chooses continuous heterosexual abstinence as a lifestyle-choice (see [Appendix 3](#) for more information)
- 10) For male subjects of reproductive potential, willingness to use a protocol-recommended method of contraception and to refrain from sperm donation from the start of study drug, throughout the study treatment period, for 90 days after administration of the last dose of any study drug, and for 6 months after the last dose of oxaliplatin or 6 months following the last dose of 5-FU whichever occurs later (see [Appendix 3](#))
- 11) Breastfeeding females must agree to discontinue nursing before study drug administration
- 12) In the judgment of the investigator, participation in the protocol offers an acceptable benefit-to-risk ratio when considering current disease status, medical condition, and the potential benefits and risks of alternative treatments for the subject's cancer
- 13) Willingness to comply with scheduled visits, drug administration plan, imaging studies, laboratory tests, other study procedures, and study restrictions
- 14) Evidence of a signed informed consent prior to implementation of any protocol specific procedure

#### **4.3. Exclusion Criteria**

Subjects who meet *any* of the following exclusion criteria are not to be randomized in this study.

- 1) Previous chemotherapy for locally advanced or metastatic gastric or GEJ cancer. Subjects may have received prior neoadjuvant or adjuvant chemotherapy as long as it was completed at least 6 months prior to randomization
- 2) Human Epidermal Growth Factor Receptor 2 (HER2)-positive gastric cancer (primary tumor or metastatic lesion). HER2-positivity is defined as either IHC3+ or IHC2+/ISH+ (ISH positivity is defined as a HER2:CEP17 ratio of  $\geq 2.0$ .)

- 3) Patients who have received palliative radiation and have not recovered from all acute, reversible effects.
- 4) Uncontrolled intercurrent illness including, but not limited to, active uncontrolled infection, active gastrointestinal bleeding, uncontrolled cardiac arrhythmia, or psychiatric illness/social situation that would limit compliance with study requirements as judged by treating physician
- 5) History of a concurrent or second malignancy except for adequately treated local basal cell or squamous cell carcinoma of the skin, cervical carcinoma in situ, superficial bladder cancer, asymptomatic prostate cancer without known metastatic disease and with no requirement for therapy or requiring only hormonal therapy and with normal prostate-specific antigen for  $\geq 1$  year prior to randomization, adequately treated Stage 1 or 2 cancer currently in complete remission, or any other cancer that has been in complete remission for  $\geq 5$  years
- 6) Major surgery, defined as any surgical procedure that involves general anesthesia and a significant incision (ie, larger than what is required for placement of central venous access, percutaneous feeding tube, or biopsy), within 28 days of first dose of study drug
- 7) Known positive status for human immunodeficiency virus (HIV)
- 8) Known acute or chronic-active infection with hepatitis B virus (HBV) or hepatitis C virus (HCV)
- 9) Peripheral neuropathy  $\geq$  Grade 2 according to National Cancer Institute Common Terminology Criteria for Adverse Events version 4.03 (NCI CTCAE v.4.03)
- 10) Chronic daily treatment with oral corticosteroids (dose of  $> 10$  mg/day methylprednisolone equivalent). Inhaled steroids and short courses of oral steroids for anti-emesis or as an appetite stimulant are allowed
- 11) Pregnant or breastfeeding women (pregnancy needs to be excluded by testing of beta-human chorionic gonadotropin [ $\beta$ -hCG])
- 12) Known or suspected central nervous system metastases
- 13) Known dihydropyrimidine dehydrogenase-deficiency (special screening not required)
- 14) Known alcohol or drug abuse or any other medical or psychiatric condition which contraindicates participation in the study
- 15) Documented myocardial infarction or unstable/uncontrolled cardiac disease (ie, unstable angina, congestive heart failure [New York Heart Association  $>$  Class II]) within 6 months of randomization
- 16) Active tuberculosis or history of latent tuberculosis that has not been treated
- 17) Any chronic medical condition that, in the opinion of the Investigator, would make the subject unsuitable for the study or would prevent compliance with the study protocol.

- 18) Serious systemic fungal, bacterial, viral, or other infection that is not controlled or requires intravenous antibiotics
- 19) Experimental medical treatment within 28 days prior to randomization
- 20) Known hypersensitivity to any of the study drugs or excipients or to Chinese hamster ovary cell products or to recombinant human or humanized antibodies, or known allergic reactions to products that contain platinum
- 21) History of long QT syndrome or whose corrected QT interval (QTc) measured using Fridericia's formula ( $QTcF = QT/RR^{0.333}$ ) at screening is prolonged ( $> 450$  ms for males and  $> 470$  ms for females)
- 22) Subjects with potassium, magnesium or calcium less than the lower limit of normal (LLN); electrolyte replacement is permitted during screening

